6. In the event that participants are unable to exercise for > 2 weeks, they will be instructed to resume their exercise at 65% of their previous exercise duration (in minutes) and 5% below the previous exercise intensity. If they fail to exercise for < 2 weeks, they will restart at the level (i.e. duration and intensity) from where they left. Then, they will follow the original recommendation of gradually increasing the exercise duration (in minutes) each week and the exercise intensity each month.

D7j. Co-interventions

Participants will continue to be followed by their treating physicians/providers for all medical care unrelated to the trial. This includes continuation of other medications as prescribed, clinic visits, and other care as usual. Specifically, use of medications, and specialist consultations (rehabilitation, pain management, and rheumatology) for fibromyalgia will be permitted (and assessed), both to adjust for co-intervention differences between arms in the analyses and to assess as secondary outcomes.

D8. DATA COLLECTION PROTOCOL

The schedule of outcomes and key variables to evaluate the effectiveness of the POYSE interventions are listed in **Table 3**. After obtaining informed consent (**Appendix 3**), a research assistant will administer a baseline assessment to gather socio-demographic data, body mass index, review the patient's history emphasizing previous treatments tried for their fibromyalgia, and administer several validated measures to assess fibromyalgia related symptoms, function, pain, and psychological status. The data collection protocol is informed by the Outcome Measures in Rheumatology Clinical Trials (OMERACT) recommendations,⁹⁷ biopsychosocial conceptual model,⁷⁹ and our previous studies.^{66,98}

To minimize the potential for ascertainment bias, the baseline and follow-up assessments will be conducted by a research assistant blinded to treatment assignment. The baseline interview will take approximately *45 minutes*, the *1, 3, 6, and 9 month* interviews about *30 minutes*. These assessments will be completed by our research assistant and generally conducted in-person, unless telephone interviews are preferred for veteran convenience. We have found that face-to-face interviews are more effective in establishing rapport. Additionally, we have found phone interviews over 30 minutes to be burdensome to both patients and interviewers. We have used a battery of measures of similar length in

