The primary outcome measure will be the **Total Score** from the **Fibromyalgia Impact Questionnaire Revised (FIQR)**. The FIQR (**Appendix 4**) has been found to be a useful brief instrument to assess the overall impact and severity of fibromyalgia.⁹⁹ The FIQR is an updated version of the widely used Fibromyalgia Impact Questionnaire (FIQ) which has been extensively used and validated in clinical trials. The FIQR consists of 21-items that assess pain, fatigue, stiffness, sleep, depression, memory, anxiety, balance, and environment sensitivity.^{9,99} All items are framed in the past 7 days and are scored on an 11-point numeric rating scores of 0 to 10, with 10 being "worst." The total score range from 0 to 100, with higher scores representing greater symptom burden and functional limitations from fibromyalgia. The FIQR has strong internal consistency (Cronbach's alpha = 0.79 to 0.93) and is comparable to the original FIQ allowing comparisons between the FIQ and FIQR.¹⁰⁰ In addition to the Total Score, the FIQR contains scales for Symptoms (10 items), Function (9 items), and Overall Impact (2 items); the most important domains in fibromyalgia trials. Scoring of the FIQR involves: 1) summing the score for function (range 0 to 90) and dividing by 3; 2) summing the score for overall impact (range 0 to 20); and 3) summing the score for symptoms (range 0 to 100) and dividing by 2. The three domains are weighted; 30% of total score ascribed to function, 50% to symptoms; and 20% for overall impact.

D8b. Measures, Schedule, and Mode of Administration

In addition to our main outcome measure (FIQR Total Score), we will also measure several other secondary outcomes recommended by the OMERACT guidelines^{97,101} and consonant with the biopsychosocial model at each follow-up assessment. These include depression, anxiety, health related quality of life, pain beliefs, fatigue, sleep, and self-efficacy. These variables are important to assess as key moderators or mediators of intervention effects. Finally, measures of fitness and physical activity as well as measures of **satisfaction and adherence to the interventions** will be assessed. We will also assess the performance of all scales to ensure they meet standard psychometric characteristics.

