Baseline patient characteristics will be evaluated with an interview adapted from our previous pain and fibromyalgia trials and will include socio-demographics, disability compensation, comorbid medical and psychiatric disorders, and prior treatments for fibromyalgia. We will also regularly assess use of other treatments for fibromyalgia (other medications, exercise, physical therapy, complementary and alternative medicine modalities, and interventional modalities) as well as prescription medication use. For medications, we will record prescribed doses, administration schedule, and number of pills prescribed, especially opioid analgesics, antidepressants, and benzodiazepines.

D8c. Description of Specific Measures

Fibromyalgia symptom severity will be assessed with the **Fibromyalgia Impact Questionnaire Revised (FIQR)**.⁹

Pain-severity: The Brief Pain Inventory is an 11-item, multidimensional pain measurement tool with demonstrated reliability in patients with arthritis as well as other pain conditions.^{102,103} The BPI rates the intensity of pain as well as the interference of pain with mood, physical activity, work, social activity, relations with others, sleep, and enjoyment of life.

Psychological symptoms are frequently associated with fibromyalgia and will be assessed by:

The PHQ-9 will be used to assess depression severity. Several studies have validated the PHQ-9 as a diagnostic measure with excellent psychometric properties.¹⁰⁴ Internal consistency has consistently been shown to be high (Cronbach's alpha > 0.80) and test-retest assessment showed the PHQ-9 to be a responsive and reliable measure of depression treatment outcomes.

The GAD-7 has demonstrated reliability (alpha = 0.89) and validity (criterion, construct, factorial, and procedural) as a measure of anxiety in the general population and primary care.¹⁰⁵

The Primary Care PTSD Screen (PC-PTSD) has been validated for use in VA primary care settings.¹⁰⁶ The sum of the 4 yes/no items yields a score ranging from 0 to 4, with scores ≥ 3 considered positive for active PTSD. Sensitivity is 78% and specificity is 87% compared to clinician interview.¹⁰⁷ In participants who screen positive, the PTSD Checklist for Military (PCL-17) will be administered. This 17-item scale assesses the DSM-IV symptoms of PTSD, and is used for diagnosis and as a severity measure as a measure of change in PTSD symptoms as a function of treatment. The PCL has demonstrated sensitivity and specificity >70%.¹⁰⁷

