Table . Outcome Assessment Protocol: Measures and Schedule of Administration

Domain	Measure	Items	Time (min)	Schedule				
				BL	1 mo	3 mo	6 mo	9 mo
Covariates	Demographics; contact information; disability compensation, comorbidity; pain treatments	36	10	X				
Fibromyalgia severity	Fibromyalgia Impact Questionnaire Revised	21	6	X	X	X	X	X
Pain Severity	Brief Pain Inventory	10	3	X	X	X	X	X
Psychological	PHQ-9 Depression	9	2	X		X		X
	GAD-7 Anxiety	7	2	X		X		X
	VA PTSD Screener	4	1	X		X		X
	VA PTSD Checklist (PCL-17)	17	4	X		X		X
Generic HRQL	Medical Outcomes SF-12	12	4	X		X		X
Fatigue	Multidimensional Fatigue Inventory	20	5	X	X	X		X
Sleep	MOS Sleep Scale	12	3	X	X	X		X

Pain beliefs	Pain Catastrophizing Scale	10	3	X		X		X
Pain coping	Centrality of Pain Scale	10	3	X		X		X
Self-efficacy	Arthritis Self Efficacy Scale	6	2	X		X		X
Treatment Response	Global Rating of Change	1	1		X	X	X	X
Physical Function and Activity	Functional Assessment which includes Fullerton Advanced Balance Scale (FAB)	18	10	X		X	X	
	Rapid Assessment of Physical Activity	8	2	X		X		X
	Activity Constraints	20	5	X		X		X
	Activities - Specific Balance Confidence Scale (ABC)	16	5	X		X		X
	Balance	7	2	X	X	X	X	X
Coherence	Sense of Coherence Scale	3	1	X		X		X
Substance Use	Illicit use and personal/family history	6	2	X				
Perceived Expectations	EXPECT Questionnaire	26	8	X	X			

Other secondary outcome measures and potential predictors of treatment response will be assessed:

The Medical Outcomes Study Short Form Questionnaire (SF-12) is the criterion standard for generic functional status and health-related quality of life.¹⁰⁸ The SF-12 assesses physical and mental functioning in 8 domains and gives reliable, valid and responsive summary scores.¹⁰⁸

The Multidimensional Fatigue Inventory (MFI) will be used to assess fatigue.¹⁰⁹ The MFI assesses clinical fatigue in 5 dimensions: general fatigue, physical fatigue, mental fatigue, reduced motivation, and reduced activity. The MFI has been validated among adults with chronic illness, chronic fatigue syndrome, and cancer, as well as among healthy adults.¹¹⁰

Sleep problems will be assessed using the MOS Sleep Scale which assesses sleep disturbance, adequacy of sleep, and sleep quantity. The MOS-Sleep Scale has demonstrated good psychometric properties in trials assessing pain.¹¹¹

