The Pain Catastrophizing Scale a 13-item scale that assesses catastrophizing—a pain belief that has been found to be strong predictor of poor treatment response.¹¹² Validation studies examining the PCS have found strong evidence of criterion-related, concurrent, and discriminant validity.¹¹²

The Centrality of Pain Scale is a 10-item measure to measure how central chronic pain is to a patient's life.¹²

The Arthritis Self-Efficacy Scale will be used to assess self-efficacy.¹¹³ This 8-item scale proved sensitive to change in our low back pain trial.¹¹⁴ For each item, patients report their degree of certainty on a scale ranging from 1 (very uncertain) to 10 (very certain).

The Patient Global Impression of Change (PGIC) is a single item measure to assess overall clinical response. This validated and reliable global rating scale is often used as the gold standard for determining clinically important differences in outcomes^{115,116} and required by the Federal Drug Administration in fibromyalgia trials. The PGIC asks subjects to rate overall improvement in symptoms using a single 7-point scale anchored by “very much improved” and “very much worsened”.

The Rapid Assessment of Physical Activity (RAPA) is a 7 item measure of physical activity for use with older adults.

The Activity Constraints is a 20-item measure which assessing seven different types of constraints on a 5-point Likert scale.

The Activities – Specific Balance Confidence Scale is a 16-item scale to assess a subject’s balance confidence in performing several activities.

The SOC-3 (3-item Sense of Coherence scale) will be used to measure the 3 dimensions salient to resilience and coherence including manageability, meaningfulness and comprehensibility.

Substance use problems will be assessed by asking questions about the use of others’ prescription drugs or street drugs.

The EXPECT Questionnaire is a 26-item measure assessing the perceived expectations of the subject for the intervention.

A Functional Assessment will consist of monitoring blood pressure, pulse, six minute walk, gait analysis, chair sit and reach test, back scratch test, chair stand test and the Fullerton Advanced Balance Scale.

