Each of the study questionnaires will be programmed into a desktop computer using Microsoft Access. The research assistant will interview the patient and enter data simultaneously into the Access program. Within the Access program, algorithms will be created to check for inappropriate or missed data entry. Computer algorithms will also automatically score the questionnaires and store the summary scales within the same database, as well as determine the appropriate date for follow-up interviews. These data will be backed up daily onto a secured server at RVAMC. Participant social security numbers, names, addresses and other personal information will be restricted to authorized personnel to protect confidentiality. For data analysis and other uses of the data, this information will be removed from the database and be replaced with a simulated identification number. This strategy has been used in our previous trials to screen and enroll patients, accurately complete follow-up assessment, and protect patient privacy. We have experience in setting up data integrity protocols and data back-up to minimize the risk for lost or inaccurate data.

D10e. Data Safety Monitoring Plan

The following multi-component Data Safety Monitoring Plan has been used in our VA RR&D-funded ESCAPE trial of OEF/OIF veterans with chronic musculoskeletal pain and NIMH-funded pain/depression SCAMP trial. Subjects are monitored during study interventions in the following ways: 1) frequent subject contacts by research team members. Responses to the interventions, as well as side effects from them are closely monitored. All interview responses are part of the study database. 2) Monthly Executive Committee Meetings. The PI and co-investigators meet monthly for Executive Committee meetings. At these meetings the investigators discuss recruitment, subject safety, protocol adherence, and any other issues that may arise. Minutes are kept and are circulated to any co-investigators not able to attend. Subjects will be allowed to withdraw from the trial at any time. If a patient withdraws, we will determine the reason for withdrawal. Possible reasons will include: 1) death, 2) worsening of comorbid medical conditions making follow-up impossible, 3) treatment side effects, and 4) other. If subjects withdraw, we will attempt to obtain their permission to complete the remaining

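### The blinded research assistant is to administer EXPECT, a questionnaire about the intervention, at month 1, which will probably reveal the arm before the 3-month primary assessment

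*Combined protocol and SAP*

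**What the plan says.** Section D9 accepts that patients cannot be blinded. Against ascertainment bias, D8 offers blinded assessment: "the baseline and follow-up assessments will be conducted by a research assistant blinded to treatment assignment". D8 continues: "These assessments will be completed by our research assistant and generally conducted in-person, unless telephone interviews are preferred for veteran convenience". The data-entry paragraph just before D10e describes how questionnaires are given: "The research assistant will interview the patient and enter data simultaneously into the Access program". That paragraph covers every study questionnaire.

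One of them concerns the treatment itself. D8c says: "The EXPECT Questionnaire is a 26-item measure assessing the perceived expectations of the subject for the intervention". Its row in the outcome schedule reads "EXPECT Questionnaire 26 8 X X", that is 26 items, 8 minutes, at baseline and 1 month. D2 counts months from the first intervention session.

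D8b adds two related kinds of information. Measures of "satisfaction and adherence to the interventions" are to be collected, and "We will also regularly assess use of other treatments for fibromyalgia", where the list includes exercise and complementary modalities. Neither statement says who collects the information, and neither names a visit.

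The primary endpoint is the FIQR total score at 3 months. The functional assessment (six-minute walk, chair stand, balance scale and others) is scheduled at baseline, 3 and 6 months.

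**The concern.** With unblinded patients, the assessor's ignorance of the arm is the only blinding the trial can claim. A patient four weeks into a yoga or exercise class, asked 26 questions aloud about expectations for the intervention, will probably let slip which one it is. If so, the assessor may know the arm before the primary visit, while the trial report describes the assessment as blinded. Knowledge of the arm could colour how FIQR questions are put and how much encouragement a patient gets in a walk or chair-stand test.

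**Working it through.** **1. Does the plan put EXPECT inside the blinded interview?** D8 assigns baseline and follow-up assessments to a blinded research assistant. The data-entry paragraph has the assistant ask and key the questionnaires. The schedule lists EXPECT among them. The mailed form in D8 is a fallback for patients who cannot be scheduled or reached. On this text EXPECT is interviewer-administered.

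**2. When could the arm be revealed?** Randomization follows the baseline interview (D6), so baseline EXPECT can reveal nothing. Month 1 can. The gap to the primary visit is 3 − 1 = 2 months; functional tests follow at months 3 and 6.

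**3. How much of the month-1 interview is this?** Scheduled minutes: FIQR 6 + Brief Pain Inventory 3 + fatigue 5 + sleep 3 + global rating 1 + balance 2 + EXPECT 8 = 28. EXPECT is 8/28 = 29%. This shows a sustained exchange about treatment; it does not measure bias.

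**4. What safeguards are stated?** D6 says that those with access to the randomization table do not assess outcomes. That protects allocation concealment, not blinding at follow-up. D9 will account for baseline expectations, which addresses the patient's expectations and not the assessor's knowledge. The available text has no separate collector for EXPECT, no rule that FIQR comes first, no request to patients not to disclose, no separate functional tester and no check on whether blinding held.

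**5. What could it do to the primary comparison?** The documents give no figure for assessor bias, so this is a sensitivity range only.

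The plan's own sample size first (D9a):
- Difference: 0.14 × 48.3 = 6.76 (the protocol prints 6.79). SD 17.6, two-sided 5%, 80% power.
- n = 2 × (1.96 + 0.84)² × 17.6² / 6.76², rounded up = 107 per arm, as stated.
- Clustering: 107 × 1.14 = 121.98, so 122 per arm. Attrition: 122 / 0.80 = 152.5, so 153 per arm and 306 in total, as stated.

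Standard error with 122 evaluable per arm: effective n = 122 / 1.14 = 107.0; SE = 17.6 × √(2 / 107.0) = 2.41. This ignores the gain from baseline adjustment.

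If assessor knowledge shifted the between-arm difference by b points with no true effect, the two-sided 5% test rejects with probability Φ(−1.96 + b/SE) + Φ(−1.96 − b/SE):

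| Assumed shift b | Share of 6.76 | Rejection under no true effect |
|---|---|---|
| 0 | 0% | 5.0% |
| 0.5 | 7% | 5.5% |
| 1 | 15% | 7.0% |
| 2 | 30% | 13.2% |
| 3 | 44% | 23.9% |

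Nothing in the documents says which row applies, or that any shift occurs.

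**The case against.** Several limits are real.

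- **The items are not shown.** If EXPECT asks only for ratings of the patient's treatment, without naming it, the answers alone need not reveal the arm. This stands: disclosure is likely, not certain.
- **Only EXPECT has a dated month-1 slot.** A reader might infer that a whole set of arm-revealing questionnaires starts then. The documents do not support that. Adherence is largely captured elsewhere: attendance records, the audio device's usage log, and practice forms and diaries collected in class (D7b, D7d, D7e, D7h). Satisfaction has no row in the schedule, which lists pain treatments at baseline only. Such items would add to the exposure only if asked in the blinded interview.
- **One person throughout is an inference.** D8 uses the singular, but D5a speaks of research assistants in the plural for baseline. If different people see a patient at months 1 and 3, what is learned at month 1 need not carry over. The plan does not arrange this.
- **The FIQR is not scored by the interviewer.** It is 21 patient-given 0–10 ratings (D8a), scored by computer algorithm. The assessor can act only through the manner of asking, and the patients know their arm anyway. This stands and is the main reason to expect a small effect on the primary endpoint. The functional tests are more exposed, but they are not primary and D9e does not name them.
- **The staff-roles text under D10c is not in the available document.** It could name a separate collector. The statements of absence above cover the available text only.

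None of this removes the conflict between blinded assessment in D8 and a treatment questionnaire given by the same role at month 1.

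**Conclusion.** The point holds in a limited form. Followed as written, the plan will probably undermine its own assessor blinding at month 1, before the 3-month primary FIQR and the functional tests at months 3 and 6. This rests on EXPECT being asked aloud, as the data-entry paragraph implies; on the answers giving away the arm, which is likely; and, for carry-over, on the same assistant seeing the patient again, which is plausible but not stated.

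The effect on the FIQR is probably small and cannot be quantified from the documents. The effort-dependent tests are more directly exposed. A reader might infer that the primary result will be biased by a point or two, or that blinding is certain to be lost by month 3; the documents establish neither. Sample size and the primary analysis are unaffected. The change is worth making because it is cheap and makes the claim of blinded assessment checkable.

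**What to change.** - Have patients complete EXPECT themselves on paper at the end of the assessment visit and seal it. Do this at baseline as well as month 1, so that the mode stays constant.
- Treat any satisfaction, adherence or treatment-use items in the same way.
- For telephone assessments, use the postage-paid envelope already described in D8. Both routes are needed because D5b expects mostly telephone assessments and D8 mostly in-person ones.
- Have staff other than the assessor enter these forms, and keep the entries off the assessor's screens.
- At each visit give FIQR first and then any scheduled functional tests.
- Ask patients not to disclose their arm.
- Have the assessor record a guessed arm at month 3, and report the guesses by arm.

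Do not hand the forms out in class: missing forms would then track attendance.

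For visits already completed, the report should state who administered EXPECT and qualify the description of blinded assessment accordingly.

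The cost is a little data-entry time and slightly more missing data on non-primary items. Because D9 uses baseline expectations in the analysis, the assistant should check the baseline form for blanks; no arm has been assigned then, so this is harmless. No new visits are needed.

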Since POYSE is not specifically powered for the secondary outcome, these results should be interpreted cautiously unless they are highly significant ($p < .001$). Pain severity as assessed by the Brief Pain Inventory will be analyzed using a repeated measurement ANCOVA model in the same way as the FIQR total score. BPI measurement at 1, 3, 6, and 9 months will be used as the response variable. Main predictors will be intervention group, time (categorical), and their interaction adjusted for the baseline BPI score. A random intercept of subject effect will be used to accommodate correlation within subject. Another random intercept of either a specific yoga or exercise group will be used to accommodate correlation within group (clustering effect for group delivered intervention).

Psychological symptoms: PHQ-9 score, GAD-7 will be analyzed using a repeated measurement ANCOVA model in the same way as the FIQR total score with repeated outcomes at 1, 3, 6, and 9 months as the response variables, the same set of main predictors and adjusted for baseline outcome measurement. The PTSD screening status will be analyzed using a generalized linear mixed model with a logit link. The main predictors will be intervention group, time (categorical) and their interaction adjusted for baseline PTSD screening status. PTSD severity from PTSD checklist for military will be analyzed similarly.

Other secondary outcome measures: The analytical strategy for other outcomes will be similar to the FIQR total score. These outcomes include SF-36, MFI, MOS Sleep Scale, Pain Catastrophizing Scale, Arthritis Self-Efficacy Scale, and PGIC.

We will employ several secondary analyses to assess the effectiveness of the treatment arms compared to each other in improving:

- Individual fibromyalgia symptoms (pain, fatigue, sleep quality, function)
- Health-related quality of life
- Patient global impression of change
- Pain beliefs and self-efficacy

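### The plan does not say which visit's screen triggers the PCL-17; if each visit's does, the between-arm PTSD-severity comparison conditions on a post-randomisation outcome

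*Combined protocol and SAP*

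**What the plan says.** - **Who gets the checklist (D8c).** "In participants who screen positive, the PTSD Checklist for Military (PCL-17) will be administered". The screen is the four-item PC-PTSD, with "scores ≥ 3 considered positive for active PTSD". No visit is named.
- **What it is for (D8c).** Besides diagnosis and severity, the checklist serves "as a measure of change in PTSD symptoms as a function of treatment".
- **When (outcome assessment table after D8c).** The row for the "VA PTSD Screener" and the row for the PCL-17 are both marked at baseline, 3 and 9 months. The PCL-17 row carries no screen-positive condition.
- **How the screen is analysed (D9e).** "The PTSD screening status will be analyzed using a generalized linear mixed model with a logit link". That model contains arm, visit and the arm-by-visit term, with the baseline screen result as a covariate.
- **How severity is analysed (D9e).** "PTSD severity from PTSD checklist for military will be analyzed similarly". No analysis set is defined, and no score is assigned to patients who screen negative.
- **Missing data (D9f).** The section deals with dropout: a mixed model under MAR, with complete-case, last-observation-carried-forward and multiple-imputation sensitivity analyses. It does not mention scores that are absent by design.

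**The concern.** An interviewer who follows D8c at month 3 has just re-administered the screener. The only rule available is to give the checklist to those who screen positive. On that reading, a patient who has improved below the cut-off has no severity score at that visit. Having a score then depends on screening status after randomisation, which D9e itself treats as an outcome that the interventions may change. The two arms would be compared on groups that are no longer the randomised ones, at odds with the intent-to-treat approach in D9c.

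If one arm helps more, it loses more of its improved patients. A real difference in PTSD severity could be understated or otherwise distorted. The gap cannot be closed at the analysis stage, because the scores would never have been collected.

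**Working it through.** **1. The plan's own figures.** The documents give no sample size, effect or screen-positive rate for the PCL-17. The only usable denominator is the trial's evaluable number from D9a, which reproduces: 107 × 1.14 = 121.98, so 122 per arm; 122 / 0.80 = 152.5, so 153 per arm and 306 in total.

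**2. Assumed inputs (none are in the documents).**
- Screen-positive rate: 20%, 35% or 50%.
- Correlation between screen and severity: 0.6 to 0.9.
- Baseline-to-follow-up correlation of severity: 0.6.
- True effect at follow-up: 0 or −0.40 SD.

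**3. Model.** Baseline severity is b ~ N(0,1). Untreated follow-up severity is f₀ = 0.6b + 0.8e. Follow-up severity is f = f₀ − effect × arm. At each visit the screen is positive if r × severity + √(1 − r²) × noise exceeds the normal quantile for the assumed rate. The arm effect is estimated by ANCOVA on b among baseline positives and among patients positive at both visits. It is also estimated as an unadjusted difference among all follow-up positives, since D9e does not restrict to patients who are positive twice. Each scenario uses 2 to 3 million simulated patients.

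**4. Uniform benefit of 0.40 SD.**

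| Positive rate, r | Baseline gate | Positive at both visits | Positive at follow-up (unadjusted) |
|---|---|---|---|
| 50%, 0.6 | −0.40 | −0.336 | −0.303 |
| 35%, 0.8 | −0.40 | −0.264 | −0.209 |
| 20%, 0.9 | −0.40 | −0.201 | −0.140 |

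Shrinkage among patients positive at both visits runs from 1 − 0.336/0.40 = 16% to 1 − 0.201/0.40 = 50%. Among all follow-up positives it runs from 1 − 0.303/0.40 = 24% to 1 − 0.140/0.40 = 65%. The baseline gate shows no bias.

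**5. Who is left (35%, r = 0.8).** At follow-up, 24% of YOGA and 35% of SEP patients screen positive. Both scores exist for 13.2% and 17.8%: 122 × 0.132 ≈ 16 YOGA patients and 122 × 0.178 ≈ 22 SEP patients. A baseline gate would keep 122 × 0.35 ≈ 43 per arm.

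**6. Non-uniform benefit (35%, r = 0.8; 0.8 SD in the affected patients only).**
- Only severe cases benefit (f₀ more than 0.6 SD above the threshold): −0.40 among patients positive at both visits, against −0.24 among all baseline positives. The estimate moves away from zero.
- Only near-threshold cases benefit (f₀ from 0.3 SD below to 0.4 SD above it): +0.04 against −0.24. The sign reverses.

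**7. No effect in any patient.** The estimate is about 0 under every gate.

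**8. Can D9f repair it?** Under an each-visit gate, no PCL-17 score exists for anyone screening negative at that visit. Multiple imputation would have nothing observed in that group to learn from. Carrying the last observation forward would give improved patients an earlier, screen-positive score. Complete-case analysis is the selected set itself.

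**The case against.** The strongest reply is that the protocol never says the gate is re-applied. A measure of change within patients needs repeat scores in the same people, which fits a baseline gate. The PCL-17 row in the table is unconditional. The screener has to be repeated anyway because screening status is an outcome in its own right, so the shared schedule is not proof. All of this stands: a reader might infer that the plan definitely selects patients after randomisation, and the text does not support that. What remains is that the text allows both readings, that the each-visit reading is the more direct one for whoever conducts the interview, and that only one of the two is safe.

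A reader might also infer that the result must be biased toward zero. That is the expected direction for a uniform benefit only; steps 6 and 7 show other outcomes.

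Nor do the documents support saying that the scores are not MAR because the patient's own low checklist score causes them to be missing. The trigger would be the PC-PTSD result, which is scheduled for everyone and so observed. The accurate criticism is that the D9e severity model does not mention the concurrent screen and that no severity scores would exist among screen-negatives to support any adjustment.

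Finally, PTSD is absent from the aims and hypotheses in Section A. D9e advises caution with secondary results, and the screening-status comparison is itself ungated. These points limit the consequence but do not settle who is to be measured.

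**Conclusion.** The point holds as a conditional one. The plan leaves open which visit's screen triggers the PCL-17, defines no analysis set for PTSD severity, and is silent on scores absent by design. Under an each-visit gate, the comparison conditions on a post-randomisation outcome and may be biased, probably toward zero if benefit is uniform (roughly 16% to 50% shrinkage among patients positive at both visits). Under a baseline gate, the set is fixed before randomisation and this bias does not arise.

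The percentages depend on assumed rates, correlations and effect, and on the choice of analysis set; only the direction and rough size should be read from them. The outcome is secondary and unpowered, and the primary FIQR analysis is not affected. The point is still worth acting on, because scores that were not collected cannot be recovered.

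**What to change.** In D8c and the outcome assessment table, state that the baseline screen alone determines who receives the PCL-17, and that every baseline-positive participant receives it at 3 and 9 months whatever the later screen shows. In D9e, name that fixed subset as the PTSD-severity analysis set and specify a linear mixed model adjusted for baseline PCL-17, with arm, time and their interaction and the random intercepts already planned for the FIQR.

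**Cost.** About 4 minutes (the table's own figure) for each baseline-positive participant who later screens negative, plus a few sentences of text. In the 35%, r = 0.8 scenario that is about (43 − 16) + (43 − 22) = 48 extra assessments per follow-up visit, or 48 × 4 = 192 minutes. The limitation is that PTSD severity is then estimated only in baseline-positive participants. Giving the PCL-17 to everyone would also avoid the selection, at a higher cost.

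**If collection is finished.** State which gate was used. If it was each visit's, report PCL-17 severity descriptively and rely on the ungated screening-status comparison for PTSD.
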